The following laboratory parameters will be analyzed with respect to Common Terminology Criteria for Adverse Events (CTCAE) grades, given in [Table 1-18](#): hemoglobin, platelets, white blood cell count, neutrophils lymphocytes, creatinine, total bilirubin (TBL), gamma-glutamyl transferase (GGT), alanine aminotransferase (ALT), aspartate aminotransferase (AST), alkaline phosphatase (ALP), glucose, cholesterol, triglycerides (TG).

The number and percentage of subjects with clinically CTCAE grade newly occurring or worsening after baseline will be presented for the treatment period.

Absolute and relative frequencies will be derived for non-overlap groups: CTCAE grade 1, CTCAE grade 2, CTCAE grade 3, and CTCAE grade 4; and exposure adjusted incidence rate will be derived for nesting groups: CTCAE grade  $\geq 1$ , CTCAE grade  $\geq 2$ , CTCAE grade  $\geq 3$ , CTCAE grade 4.

**Table 1-18 CTCAE grades for laboratory parameters to be analyzed**

| CTCAE v4.0 Term                    | Grade 1                                  | Grade 2                                 | Grade 3                            | Grade 4               |
|------------------------------------|--|---|------------------------------------|-----------------------|
| HGB decreased (Anemia)             | <LLN - 6.2 mmol/L                        | <6.2 - 4.9 mmol/L                       | <4.9 mmol/L                        |                       |
| Platelet count decreased           | <LLN - 75.0 x10e9 /L                     | <75.0 - 50.0 x10e9 /L                   | <50.0 - 25.0 x10e9 /L              | <25.0 x 10e9 /L       |
| White blood cell decreased         | <LLN - 3.0 x 10e9 /L                     | <3.0 - 2.0 x 10e9 /L                    | <2.0 - 1.0 x 10e9 /L               | <1.0 x 10e9 /L        |
| Neutrophil count decreased         | <LLN - 1.5 x 10e9 /L                     | <1.5 - 1.0 x 10e9 /L                    | <1.0 - 0.5 x 10e9 /L               | <0.5 x 10e9 /L        |
| Lymphocyte count decreased         | <LLN - 0.8 x 10e9/L                      | <0.8 - 0.5 x 10e9 /L                    | <0.5 - 0.2 x 10e9 /L               | <0.2 x 10e9 /L        |
| Creatinine increased*              | >1 - 1.5 x baseline;
>ULN - 1.5 x ULN | >1.5 - 3.0 x baseline; >1.5 - 3.0 x ULN | >3.0 baseline;
>3.0 - 6.0 x ULN | >6.0 x ULN            |
| TBL increased                      | >ULN - 1.5 x ULN                         | >1.5 - 3.0 x ULN                        | >3.0 - 10.0 x ULN                  | >10.0 x ULN           |
| GGT increased                      | >ULN - 2.5 x ULN                         | >2.5 - 5.0 x ULN                        | >5.0 - 20.0 x ULN                  | >20.0 x ULN           |
| ALT increased                      | >ULN - 3.0 x ULN                         | >3.0 - 5.0 x ULN                        | >5.0 - 20.0 x ULN                  | >20.0 x ULN           |
| AST increased                      | >ULN - 3.0 x ULN                         | >3.0 - 5.0 x ULN                        | >5.0 - 20.0 x ULN                  | >20.0 x ULN           |
| ALP increased                      | >ULN - 2.5 x ULN                         | >2.5 - 5.0 x ULN                        | >5.0 - 20.0 x ULN                  | >20.0 x ULN           |
| Glucose increased (Hyperglycemia ) | ;  | >ULN - 8.9 mmol/L                       | >8.9 - 13.9 mmol/L                 | >27.8 mmol/L          |
| Glucose decreased (Hypoglycemia)   | <LLN - 3.0 mmol/L                        | <3.0 - 2.2 mmol/L                       | <2.2 - 1.7 mmol/L                  | <1.7 mmol/L           |
| Cholesterol high                   |  | >ULN - 7.75 mmol/L                      | >7.75 - 10.34 mmol/L               | >10.34 - 12.92 mmol/L |
| Hypertriglyceridemia               | 1.71 - 3.42 mmol/L                       | >3.42 - 5.7mmol/L                       | >5.7 - 11.4 mmol/L                 | >11.4 mmol/L          |

\*Note: for “creatinine increased” the baseline criteria do not apply

Shift tables will be presented comparing baseline laboratory result (CTCAE grade) with the worst results (expressed in CTCAE grade) during the treatment phase (either initial or entire) analyzed. Of note, baseline will be defined as last assessment prior to first dosing in the core study. Subjects with abnormal laboratory values will be listed and values outside the normal ranges will be flagged.

Exposure adjusted incidence rate for neutropenia CTCAE grade  $\geq 2$  will be presented for the entire treatment period.

Summaries for newly occurring or worsening clinically notable lipid abnormalities will also be provided cumulatively for each of the following parameters and categories:

- HDL:
  - $\leq$ LLN
  - $<0.8 \times$  LLN
- LDL, cholesterol, triglycerides:
  - $\geq$ ULN
  - $>1.5 \times$  ULN
  - $>2.5 \times$  ULN

Subjects with newly occurring or worsening after baseline abnormalities in lipid parameters will be listed. If a subject experiences newly occurring or worsening of abnormality for a parameter the entire time course of that parameter will be listed.

Newly occurring liver enzyme abnormalities will also be summarized based on the event criteria given in [Table 1-19](#).

**Table 1-19 Liver-related events**

| Parameter              | Criterion  |
|------------------------|--|
| ALT                    | >3xULN; >5xULN; >8xULN; >10xULN, >20xULN   |
| AST                    | >3xULN; >5xULN; >8xULN; >10xULN; >20xULN   |
| ALT or AST             | >3xULN; >5xULN; >8xULN; >10xULN; >20xULN   |
| TBL                    | >1xULN; >1.5xULN; >2xULN; >3xULN,  |
| ALP                    | >1.5xULN; >2xULN; >3xULN; >5xULN   |
| ALT or AST & TBL       | ALT or AST >3xULN & TBL >1.5xULN;
ALT or AST >3xULN & TBL >2xULN;
ALT or AST >5xULN & TBL >2xULN;
ALT or AST >8xULN & TBL >2xULN;
ALT or AST >10xULN & TBL >2xULN
ALT or AST >20xULN & TBL >2xULN   |
| ALP & TBL              | ALP >3xULN & TBL >2xULN
ALP >5xULN & TBL >2xULN   |
| ALT or AST & TBL & ALP | ALT or AST >3xULN & TBL >2xULN & ALP ≤ 2xULN ( Potential Hy's Law )
Note: elevated ALP may suggest obstruction as a consequence of gall bladder or bile duct disease; ALP may also be increased in malignancy. FDA therefore terms Hy's Law cases as indicators of pure hepatocellular injury . This does not mean that cases of ALT or AST >3xULN & TBL >2xULN & ALP >2xULN may not result in severe DILI. |

**Notes:**

- 1) In studies which enroll subjects with pre-existing liver disease, baseline LFT may be increased above ULN; in such a case it is meaningful to add the condition "and worse than baseline" to the abnormality criteria
- 2) In case an Adjudication Committee is in place it may be meaningful to summarize all abnormalities classed as e.g., *definitely/probably* (depending on the categories used) related to study treatment

For a combined criterion to be fulfilled, all conditions have to be fulfilled on the same visit. The criteria are not mutually exclusive, e.g., a subject with ALT = 6.42xULN is counted for ALT >3xULN and ALT >5x ULN.

Individual subject data listings will be provided for subjects with abnormal laboratory data. Data of subjects with newly occurring liver enzyme abnormalities will be listed in an additional listing.

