7.3 Liver safety monitoring

To ensure patient safety and enhance reliability in determining the hepatotoxic potential of an investigational drug, a standardized process for identification, monitoring and evaluation of liver events has to be followed.

Liver events are divided into two categories:

- Liver events of special interest (AESI) which consist of LFTs elevations
- Medically significant liver events which are considered as serious adverse events (SAEs) and which consist of marked elevations of LFTs and / or pre-specified adverse events.

Please refer to [Table 14-1](#) in [Appendix 2](#) for complete definitions of liver events.

Any liver event which meets the criteria for “medically significant” event as outlined in [Table 14-1](#) of [Appendix 2](#) should follow the **standard procedures for SAE reporting** as described in [Section 7.2](#).

Every liver event as defined in [Table 14-1](#) of [Appendix 2](#) should be followed up by the investigator or designated personal at the trial site as summarized below. Detailed information is outlined in [Table 14-2](#) in [Appendix 2](#).

- Repeating the LFT to confirm elevation as appropriate
- Discontinuation of the investigational drug if appropriate
- Hospitalization of the patient if appropriate
- A causality assessment of the liver event via exclusion of alternative causes (e.g., disease, co-medications)
- An investigation of the liver event which needs to be followed until resolution.

These investigations can include serology tests, imaging and pathology assessments, hepatologist's consultancy, based on investigator's discretion. All follow-up information, and the procedures performed should be recorded on appropriate CRF pages, including the liver event overview CRF pages.

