Newcombe RG (1998) Two-sided confidence intervals for the single proportion: comparison of seven methods. *Statistics in Medicine*; 17: 857-872.

WHO regional office for Europe, Nutrition Unit. (1988) Classification and description of anthropometric data. EUR/ICP/NUT/125 document. Copenhagen, Denmark.

13 Appendix 1: Clinically notable laboratory values and vital signs

The following criteria will be used to define expanded limits and notable abnormalities of key laboratory tests. Notable values for blood pressure and pulse are presented in [Section 6.5.2](#). Whether action needs to be taken to address notable laboratory or vital signs values will be decided by the investigator, taking into account the overall status of the subject. No specification is foreseen as part of the study protocol.

Liver Function and Related Variables

Alanine transaminase (ALT) (SGPT):	> 3 x Upper Limit of Normal (ULN)
Aspartate transaminase (AST) (SGOT):	> 3 x ULN
Total bilirubin:	> 2 x ULN
Alkaline phosphatase:	> 2.5 x ULN

Renal Function and Electrolyte Variables

Creatinine (serum):	> 1.5 x ULN
Potassium:	> 6 mmol/L or < 3 mmol/L
Sodium:	> 160 mmol/L or < 115 mmol/L

Hematology Variables

Hemoglobin:	≥ 20 g/dL decrease from baseline
Platelet count:	< Lower Limit of Normal (LLN)
White blood cell count:	< 0.8 x LLN
Neutrophils:	< 0.9 x LLN
Eosinophils:	> 1.1 x ULN
Lymphocytes:	> 1.1 x ULN

Urinalysis Variable

Protein urine dipstick:	++*
-------------------------	-----

* ++ is ≥ 100 mg/dL

14 Appendix 2: Liver event definitions and follow-up requirements

Table 14-1 Liver Event Definitions

	Definition/ threshold
Adverse event of special interest	
Laboratory values	ALT or AST > 3 x ULN ALP > 2 x ULN TBL > 1.5 x ULN
Medically significant event (SAE)	
Laboratory values	ALT or AST > 5 x ULN (with or without TBL > 2 x ULN [mainly conjugated fraction]) ALP > 5 x ULN (with or without TBL > 2 x ULN [mainly conjugated fraction]) TBL > 3 x ULN Potential Hy's Law cases (defined as ALT/AST > 3 x ULN and TBL > 2 x ULN [mainly conjugated fraction] without notable increase in ALP to > 2 x ULN)

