Adverse events	Any clinical event of jaundice (or equivalent term) ALT or AST > 3 x ULN accompanied by general malaise, fatigue, abdominal pain, nausea, or vomiting, or rash with eosinophilia Any event that links to a preferred term (PT) in the MedDRA dictionary falling under the SMQ sub-module "Drug-related hepatic disorders – severe events only" or any "Hy's law case" PT

* These events cover the following: hepatic failure, fibrosis and cirrhosis, and other liver damage-related conditions; the non-infectious hepatitis; the benign, malignant and unspecified liver neoplasms

Table 14-2 Liver Event Follow Up Requirements

Criteria	Event type	Actions required	Follow-up monitoring
Potential Hy's Law case ^a	Medically significant	Discontinue the study drug immediately Hospitalize, if clinically appropriate Report to Novartis as an SAE Establish causality	ALT, AST, TBL, Alb, PT, ALP and γGT until resolution ^c (frequency at investigator discretion)
ALT or AST			
> 8 x ULN	Medically significant	Repeat LFT within 48 hours If elevation persists, discontinue the study drug immediately Hospitalize if clinically appropriate Report to Novartis as an SAE Establish causality	ALT, AST, TBL, Alb, PT, ALP and γGT until resolution ^c (frequency at investigator discretion)
> 5 to ≤ 8 x ULN	Medically significant	Repeat LFT within 48 hours If elevation persists for more than 2 weeks , discontinue the study drug Report to Novartis as an SAE Establish causality	ALT, AST, TBL, Alb, PT, ALP and γGT until resolution ^c (frequency at investigator discretion)
> 3 x ULN accompanied by symptoms ^b	Medically significant	Discontinue the study drug immediately Hospitalize if clinically appropriate Report to Novartis as an SAE Establish causality	ALT, AST, TBL, Alb, PT, ALP and γGT until resolution ^c (frequency at investigator discretion)
> 3 to ≤ 5 x ULN (patient is asymptomatic)	AESI	Central laboratory to report to Investigator & Novartis Repeat LFT once or twice in the week If elevation persists, establish causality	Investigator discretion Monitor LFT within 1 to 4 weeks or at next visit
≤ 3 x ULN (patient is asymptomatic)	N/A	Repeat LFT at next visit	
ALP (isolated)			
> 5 x ULN	Medically significant	Repeat LFT within 48 hours If elevation persists, report to Novartis as an SAE Establish causality	Investigator discretion Monitor LFT within 1 to 4 weeks or at next visit

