> 2 to ≤ 5 x ULN (patient is asymptomatic)	AESI	Central laboratory to report to Investigator & Novartis	Investigator discretion Monitor LFT within 1 to 4 weeks or at next visit

Criteria	Event type	Actions required	Follow-up monitoring
		Repeat LFT once or twice in the weekIf elevation persists, establish causality	
≤ 2 x ULN (patient is asymptomatic)	N/A	Repeat LFT at next visit	
TBL (isolated)			
> 3 x ULN	Medically significant	Repeat LFT within 48 hours If elevation persists, discontinue the study drug immediately Hospitalize if clinically appropriate Report to Novartis as an SAE Establish causality	ALT, AST, TBL, Alb, PT, ALP and γGT until resolution ^c (frequency at investigator discretion) Test for hemolysis (e.g., reticulocytes, haptoglobin, unconjugated [indirect] bilirubin)
> 1.5 to ≤ 3 x ULN (patient is asymptomatic)	AESI	Central laboratory to report to Novartis Repeat LFT once or twice in the weekIf elevation persists, establish causality	investigator discretion Monitor LFT within 1 to 4 weeks or at next visit
≤ 1.5 x ULN (patient is asymptomatic)	N/A	Repeat LFT at next visit	
Preferred terms			
Jaundice	Medically significant	Discontinue the study drug immediately Hospitalize the patient Report to Novartis as an SAE Establish causality	ALT, AST, TBL, Alb, PT, ALP and γGT until resolution ^c (frequency at investigator discretion)
“Drug-related hepatic disorders - severe events only” SMQ AE	Medically significant	Discontinue the study drug hospitalization if clinically appropriate Report to Novartis as an SAE Establish causality	Investigator discretion

^a Elevated ALT/AST > 3 x ULN and TBL > 2 x ULN but with no notable increase in ALP to > 2 x ULN

^b General malaise, fatigue, abdominal pain, nausea, or vomiting, rash with eosinophilia

^c Resolution is defined as an outcome of one of the following: return to baseline values, stable values at three subsequent monitoring visits at least 2 weeks apart, remain at elevated level after a maximum of 6 months, liver transplantation, and death.

15 Appendix 3: Blood collection log for pharmacokinetics (PK) and immunogenicity (IG)

Table 15-1 Blood collection log for PK

Visit Name	Time point	Volume (approx .)	Analyte	Sample number	Dose Reference ID/ PK collection number**
Week 52 ¹	Pre-dose	(2 mL)	AIN457 for PK	(5)	(5)
Week 64	Pre-dose	2 mL	AIN457 for PK	7	7
Week 76	Pre-dose	2 mL	AIN457 for PK	8	8
Week 104	Pre-dose	2 mL	AIN457 for PK	9	9
Week 116	Pre-dose	2 mL	AIN457 for PK	10	10

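### SAP 1.9.2 counts combined liver criteria, including potential Hy's Law, only when all limits are crossed on the same visit, so an event whose bilirubin crossing follows its ALT/AST crossing can be left out of the combined rows

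*SAP*

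**What the plan says.** SAP 1.9.2, Table 1-19, lists single-parameter liver criteria (ALT, AST, TBL, ALP) and combined criteria. The potential Hy's Law row is "ALT or AST >3xULN & TBL >2xULN & ALP ≤ 2xULN". The notes below the table add: "For a combined criterion to be fulfilled, all conditions have to be fulfilled on the same visit". They also promise an additional listing of subjects with newly occurring liver enzyme abnormalities.

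Protocol Appendix 2 defines the same event in footnote a to Table 14-2: "Elevated ALT/AST > 3 x ULN and TBL > 2 x ULN but with no notable increase in ALP to > 2 x ULN". Table 14-1 has the same limits, adds that the bilirubin should be mainly conjugated, and classes the event as medically significant. Neither place says that the values must come from one draw or one visit.

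Table 14-2 treats a liver abnormality as a course over time. For several categories the action is "Repeat LFT within 48 hours". Others call for one or two repeats in the week, or monitoring of ALT, AST, TBL and ALP until resolution. Protocol 7.3 separately refers to "Medically significant liver events which are considered as serious adverse events (SAEs) and which consist of marked elevations of LFTs" and sends these events through SAE reporting.

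**The concern.** Long-term safety is the primary objective, and the potential Hy's Law row is the table entry that summarises possible hepatocellular injury. If bilirubin rises as the transaminases are already falling, the two limits are crossed on different draws of one event. The same-visit rule then counts the two crossings only separately. A narrative or SAE report of a potential Hy's Law case, valid under the protocol's wording, could sit beside a Table 1-19 count of zero.

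A second problem is operational. The rule depends on what a visit is, and the SAP offers more than one possible meaning. The answer could change the count, and could change it differently between dosing groups.

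**Working it through.** The plan gives no figure for this point, so none can be reproduced. The check is one of logic and of window arithmetic.

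**1. Does the rule omit a subject who crosses all the limits?** Take an assumed subject with two draws (values in multiples of ULN):

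| Draw | ALT | TBL | ALP |
|---|---|---|---|
| First | 7.0 | 1.2 | 1.1 |
| Second | 2.6 | 2.8 | 1.2 |

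- Same-visit rule, first draw: ALT 7.0 > 3, but TBL 1.2 is not above 2, nor above 1.5. No combined row is met.
- Same-visit rule, second draw: TBL 2.8 > 2, but ALT 2.6 is not above 3. No ALT/AST row is met, and ALP 1.2 is not above 3, so no ALP & TBL row is met.
- Draws allowed to differ: highest ALT 7.0 > 3, highest TBL 2.8 > 2, and ALP at most 2 throughout. Potential Hy's Law is met.
- Single-parameter rows in either case: ALT >3x and >5xULN; TBL >1x, >1.5x and >2xULN.

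The subject is therefore visible in the table but absent from all its combined rows.

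**2. Does SAE reporting always cover the gap?** In the example, ALT above 5xULN is itself medically significant in Table 14-1. Now take an asymptomatic subject with ALT between 3 and 5xULN and, on a later draw, TBL between 2 and 3xULN. Each value alone is an event of special interest in Table 14-1. The event becomes an SAE on laboratory grounds only if the two draws are read together as potential Hy's Law. SAE reporting may show such a subject, but this is not certain.

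**3. What is a visit?** SAP 1.4.4 maps scheduled and unscheduled assessments into analysis windows for data summarised by visit. Table 1-9 takes the most extreme value in the window for notable abnormalities and CTCAE grades. Liver criteria are not named there. Window length = last day − first day + 1, from Table 1-8:

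| Group after Week 156 | Window | Days | Length |
|---|---|---|---|
| Start of relapse | Week 160 | 1108–1135 | 28 |
| Start of relapse | Week 164 | 1136–1163 | 28 |
| Every four weeks | Week 168 | 1108–1219 | 112 |
| Every four weeks | Week 180 | 1220–1303 | 84 |
| Every four weeks | Week 192 | 1304–1401 | 98 |
| Every four weeks | Week 260 | 1766–1835 | 70 |

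Suppose ALT crosses on Day 1121 and TBL on Day 1149, which is 28 days later.

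- Visit = sample date: the pair is counted in no group.
- Visit = Table 1-8 window with the most extreme value: the pair is counted under every-four-week dosing (both days lie in 1108–1219). It is not counted under start-of-relapse dosing (the days lie in 1108–1135 and 1136–1163).
- Visit = combined window: SAP 1.4.4 merges windows for parameters not collected at every visit. As Table 6-1 reads, the first scheduled chemistry draw after Week 156 is at Week 180. Merging up to it gives Days 1108–1275 (168 days) for start of relapse and 1108–1303 (196 days) for the other groups. The pair is then counted in both, but so would be values many weeks apart.

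The same data thus give three different answers, depending on a definition that the SAP does not supply.

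**4. Direction.** A row that allows TBL to follow ALT/AST within a fixed interval, with ALP read at the ALT/AST draw, contains every same-date case (interval zero). The same-date count can only be equal or lower, and the difference between the two rows is exactly the number of subjects at issue.

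**The case against.** The protocol is silent on timing, so the SAP contradicts no protocol wording. It has pre-specified one tabulation rule, and it drops the protocol's conjugated-bilirubin qualifier, which makes it broader in that respect. Table 1-19 also has a combined row at TBL >1.5xULN, and the repeat tests in Table 14-2 make it more likely that a simultaneous crossing is captured. If a visit means a window, nearby draws may combine anyway. All of this stands, and it means that the rule is a choice and not a contradiction. It does not supply the missing combined count or settle what a visit is.

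A reader might go further and infer that the SAP misses the most serious liver cases, or that one missed case would change the trial's conclusion. The documents do not support either. The subject remains in the single-parameter rows and the liver listing and, where a medically significant limit is met, in SAE reporting. The plan tests no hypothesis (SAP 1.8.3) and gives no expected number of Hy's Law cases.

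**Conclusion.** The point holds as a low-cost improvement. The same-visit rule is narrower than the protocol's definition as worded, does not fit easily with the serial testing that the protocol foresees, and is not tied to a sample date or a window. It can understate the combined rows and cannot overstate them relative to a time-window row. The size cannot be computed: the documents give 675 enrolled subjects but no liver-event rate and no distribution of the time between ALT and TBL crossings. The laboratory values in the examples are assumptions chosen to show the mechanism.

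A reader might also infer a defect from Table 1-18, where glucose jumps from ">8.9 - 13.9 mmol/L" in Grade 3 to above 27.8 mmol/L in Grade 4, and cholesterol Grade 4 stops at ">10.34 - 12.92 mmol/L". This cannot be asserted. The Grade 1 cell for glucose holds only a semicolon and that for cholesterol is empty, which fits a table damaged in conversion from PDF. Even as printed, glucose above 27.8 mmol/L is Grade 4, and cholesterol is also summarised in open-ended multiples of ULN. For an assumed ULN of 4.5 to 6.2 mmol/L, 12.92 mmol/L is 12.92/4.5 = 2.87 to 12.92/6.2 = 2.08 times ULN, so any higher value falls in the >1.5xULN category. At most, these two rows should be checked against the original PDF.

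**What to change.** In SAP 1.9.2, notes to Table 1-19:

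- Keep the same-visit count, and define same visit as the same sample date.
- For the ALT/AST & TBL rows and the potential Hy's Law row, add a second row. It counts subjects with any draw above the ALT/AST limit and a TBL value above its limit on that date or within a pre-stated interval after it. Thirty days would serve as an example. It is an assumption, since the documents give no interval.
- Use scheduled and unscheduled draws, and the same interval in all treatment groups, without reference to analysis windows.
- For potential Hy's Law, read ALP at the qualifying ALT/AST draw.

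This is a counting rule only and changes nothing in patient management. The cost is a few lines of SAP text and a small programming change. The drawback is that an unrelated ALT/AST and TBL pair may occasionally be flagged. The existing liver listing will show such pairs, and the same-date row beside it keeps the stricter count available.
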